#### **7.5. Primary Safety Analyses**

The hypothesis for the primary safety endpoint is that the Active NW System will not lead to worsening of daytime sleepiness as measured by the Epworth Sleepiness Scale, which provides a score between 0 and 24 with higher values indicating a higher degree of sleepiness. Specifically, the hypothesis is that on-average a user of NW will have a mean ESS score measured at 30 days following the start of NW digital therapeutic system use that is not higher than their ESS score measured at baseline. This hypothesis will be tested similarly to the primary efficacy hypothesis using a one sample t-test.

The hypothesis for the secondary safety endpoint is that the Active NW System will not lead to an increase in suicide risk as assessed by Columbia-Suicide Severity Rating Scale (C-SSRS) from baseline (Day 0) to Day 30. C-SSRS has ratings of "none", "low", "moderate", and "high". Those possible participants rated as "high" on the C-SSRS at Visit 1 will NOT qualify for the study and, if deemed necessary by the PI, will be given immediate assessment by a licensed Mental Health Provider, who will determine the next therapeutic steps. This hypothesis will be tested similarly to the primary efficacy hypothesis using a one sample t-test.

#### **7.6. Secondary/Exploratory Analyses**

Secondary and Exploratory analyses will be carried out with appropriate regression modeling techniques and hypothesis tests. In particular, we will use longitudinal data analysis methods, such as generalized estimating equations and generalized linear mixed models, to assess temporal variation in the longitudinal outcome measures, and we will carry out two sample t-tests of the secondary hypotheses.

At the conclusion of the trial, the data will be assessed as both intention to treat (ITT) and per protocol. The effect sizes at the conclusion of the analyses will be compared using standard techniques. If the effect size of the per protocol analysis is greater than 10%, data will be reported as intention to treat to decrease probability of type I errors. Both analyses will follow the outline below:

Secondary outcomes, data will be presented as mean(standard deviation) or median (interquartile range), as appropriate for continuous variables. Categorical variables will be presented as frequency

(percentage). Continuous data will be assessed for normality, and transformed as appropriate (e.g. log transformation, square root transformation, etc.). Patient demographics and characteristics will be listed and compared. Continuous variables will be analyzed by category, intervention vs control, by two-sided t-test or Mann-U Whitney, as appropriate. Categorical variables will be compared by Chi-Square test or Fisher's Exact test as appropriate. Longitudinal data will be analyzed by repeated measures tests as appropriate for the variables.

Repeated measure ANOVA will be used to determine the difference in responses at the time points between groups for all survey types and questions, as appropriate. If determined inappropriate Poisson regression models will be used to determine the univariate, univariable, effect size.

Upon secondary outcomes analysis, multivariable, adjusted, models will be used to determine controlled effect sizes. Each variable with a p-value of 0.25 or less in standard distribution test will be included in the model. Backward stepwise regression modeling may be used to best fit the model.

Time-to-event analyses will be conducted to determine time to survey effects over the longevity of the study (baseline, visit 2, day 30, day 60, day 90) for all survey results within the secondary outcomes. Univariate Cox regression models may be used to determine hazard ratios for the survey scores if appropriate.

Correlation coefficients (i.e. Spearman, Pearson) may be used to determine the inter-survey reliability. If determined to be reliable, multivariate analyses may be conducted for surveys.

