### 5.1. Inclusion Criteria

#### Inclusion Criteria

- Either Diagnosis of PTSD via American Psychiatric Association PTSD diagnostic criteria in the fifth edition of its Diagnostic and Statistical Manual of Mental Disorders (DSM-5) or having symptoms consistent with PTSD (subject must score at least 25 on the PTSD Checklist-5 to qualify for the study).
- Equal to or older than 22 years of age.
- Proficient in both reading and writing in the English language.
- Pittsburgh Sleep Quality Index (PSQI). Potential participants would need to score 10 or more to qualify.
- ESS: On question #8 any score above “0” will prompt an additional question:
  - Do you drive (“get behind the wheel”) when you are drowsy?
    - Answer must be “No” to be enrolled in the study due to safety concerns.
- Have repetitive nightmares contributing to disrupted sleep as reported by the subject
- Wireless Internet and two power outlets where they sleep
- Prazosin use; if yes, subject may be included if willing to be tapered by prescribing provider.
  - Taper must be completed, and the subject must be off prazosin for 2 weeks prior to enrollment.
- Alpha blocker use; if yes, subject may be included if willing to be tapered by prescribing provider. Taper must be completed, and the subject must be off all alpha blockers for 2 weeks prior to enrollment.

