**Figure 4: Power Curve (total completers-  $n=120$ , 50% for each arm)**

The rationale for powering the trial to detect a 3-point reduction is two-fold. First, a 3-point reduction constitutes a clinically relevant benefit as this may reflect, for example, a change from 3 (most severe) to 0 (least severe) on a particular item of the PSQI, or a 1-point reduction on three items of the PSQI. Second, assuming a 5-point standard deviation, the targeted 3-point reduction is equivalent to a 0.6 standardized effect, which is plausible as evidenced by a meta-analysis for the observed benefit in previous clinical trials evaluating cognitive behavioral therapies for treating nightmare disorder using the difference between PSQI score at baseline and post-treatment follow-up assessment in which the estimated standard effect size was estimated to be 0.68 (0.34, 1.03). Furthermore, a more recent open-label trial reported a standardized effect size of 1.06. Therefore, the targeted 3-point reduction or 0.6 standardized effect constitutes both a plausible and clinically meaningful benefit in this context.

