All measures used in this study will be evaluated using an intention-to-treat analysis; that is, all study participants completing the study will be included in the data analysis in the group to which they were assigned at enrollment. Additionally, a per-protocol analysis will be completed for all measures used in the study. For this analysis, use of the study device at least 50% of the study nights during the first 30 nights of the study will constitute adequate adherence to the study treatment.

The Trauma-Related Nightmare Scale questionnaire is not designed to produce a score when it is administered. The individual questions on this scale will be evaluated separately from one another.

Missing data is inevitable and can be handled in multiple ways. The data will need to be evaluated to determine the randomness of the missing data. First we will identify the distribution of the missing values and their impact then we will determine a path to deal with missing data. Depending on the impact of the missing values, we will omit participants without full data, omit missing values, impute missing values with the mean, or use multiple imputation.

Secondary and Exploratory analyses will be carried out with appropriate regression modeling techniques and hypothesis tests. In particular, we will use longitudinal data analysis methods, such as generalized estimating equations and generalized linear mixed models, to assess temporal variation in the longitudinal outcome measures, and we will carry out two sample t-tests of the secondary hypotheses. At the conclusion of the trial, the data will be assessed as both intention to treat (ITT) and per protocol. The effect sizes at the conclusion of the analyses will be compared using standard techniques. If the effect size of the per protocol analysis is greater than 10%, data will be reported as intention to treat to decrease probability of type I errors. Both analyses will follow the outline below:

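### The only named replacement for repeated-measures ANOVA on the questionnaires is a plain univariable Poisson model, whose standard errors are wrong whenever variance differs from the mean

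*Protocol*

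**What the plan says.** Protocol section 7.6 plans repeated-measures ANOVA to compare responses over time "between groups for all survey types and questions", where appropriate. The next sentence gives the alternative: "If determined inappropriate Poisson regression models will be used to determine the univariate, univariable, effect size". The SAP repeats this sentence in its text on secondary outcomes and adds no detail.

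Neither document states:
- a criterion for judging ANOVA inappropriate;
- an overdispersion check, scale parameter, quasi-Poisson or negative binomial option, or robust variance;
- how repeated measurements on one participant would enter the Poisson model.

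Section 7.6 also mentions longitudinal methods "such as generalized estimating equations and generalized linear mixed models, to assess temporal variation", but does not link them to this fallback. Separately, it keeps two-sample t-tests for the secondary hypotheses, and t-tests or Mann-Whitney tests for continuous variables.

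The outcomes covered are rating scales. The Epworth scale, for example, "provides a score between 0 and 24 with higher values indicating a higher degree of sleepiness". The nightmare survey has no total score, and the SAP says of it: "The individual questions on this scale will be evaluated separately from one another".

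**The concern.** Poisson regression ties the variance to the mean. A bounded sum of rating items has no reason to obey that relation. Where the spread is larger than Poisson allows, the reported standard error is too small and the interval too narrow. Where it is smaller, the reverse holds.

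Two further features follow from the wording. A univariable model has no baseline term. As written, it also ignores within-person correlation, although it stands in for a repeated-measures method. Nor can it be fitted to the change scores by which protocol section 3 defines the secondary outcomes, because changes can be negative. It would have to use raw scores.

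At stake are the intervals and p-values that might accompany effect sizes for PTSD symptoms, depression, insomnia, quality of life and nightmares, should the fallback be used.

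**Working it through.** **The plan's own figure.** The documents give no operating characteristic for the Poisson fallback. The figure they do give is 90% power for the primary t-test with 60 completers per arm, a difference of 3 and an SD of 5. The standard error is 5 × √(2/60) = 0.913, and 3/0.913 = 3.286. Power is Φ(3.286 − 1.96) = 90.8%, or 90.3% with the noncentral t. The figure reproduces and does not depend on the point made here.

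**Inputs**
- From the documents: 60 completers per arm; two-sided alpha 0.05; Epworth range 0-24. The only SD is 5 points ("assuming a 5-point standard deviation, the targeted 3-point reduction is equivalent to a 0.6 standardized effect"), and it refers to PSQI change. Entry floors are, for PSQI, "Potential participants would need to score 10 or more to qualify", and for PCL-5, "subject must score at least 25 on the PTSD Checklist-5 to qualify for the study".
- Assumed: every mean; every SD for a raw score, including use of the 5 points for PSQI scores; the 0-3 range for a single item.

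**Formulas.** For one visit, with arm as the only term, the Poisson estimate is the log ratio of arm means. With n per arm, mean m and standard deviation SD:
- Poisson SE = √(2/(n·m))
- true SE ≈ (SD/m)·√(2/n)
- Poisson SE / true SE = 1/√φ, where φ = SD²/m
- actual two-sided type I error = 2·[1 − Φ(1.96/√φ)]

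Worked case, m = 12, SD = 5, n = 60: Poisson SE = √(2/720) = 0.0527; true SE = (5/12) × √(2/60) = 0.0761; ratio 0.69. Here φ = 25/12 = 2.083, so the type I error is 2·[1 − Φ(1.96/1.443)] = 17.4%.

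| Assumed score | φ | Poisson SE / true SE | Type I error |
|---|---|---|---|
| PSQI, mean 8, SD 5 | 3.13 | 0.57 | 26.8% |
| PSQI, mean 12, SD 5 | 2.08 | 0.69 | 17.4% |
| PSQI, mean 16, SD 5 | 1.56 | 0.80 | 11.7% |
| PSQI, mean 12, SD 3 | 0.75 | 1.15 | 2.4% |
| Epworth, mean 10, SD 5 | 2.50 | 0.63 | 21.5% |
| PHQ-9, mean 12, SD 5 | 2.08 | 0.69 | 17.4% |
| ISI, mean 16, SD 4 | 1.00 | 1.00 | 5.0% |
| PCL-5, mean 45, SD 8 | 1.42 | 0.84 | 10.0% |
| PCL-5, mean 45, SD 15 | 5.00 | 0.45 | 38% |
| PCL-5, mean 40, SD 15 | 5.63 | 0.42 | 40.9% |
| 0-3 item, mean 1.5, SD 1.0 | 0.67 | 1.22 | 1.6% |

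The error changes sign at SD = √m: about 3.5 for a mean of 12, 6.3 for a mean of 40 and 1.2 for a mean of 1.5.

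**Simulation check** (60 per arm, no true difference, rounded and bounded scores, 4,000 runs per case). The plain Poisson SE rejected in 16.3% of runs (mean 12, SD 5), 20.5% (mean 10, SD 5), 40.7% (mean 40, SD 15), 2.0% (mean 12, SD 3) and 1.2% (0-3 item). Across all six cases run, the same model with a robust variance rejected in 4.9-5.8%, and the t-test in 4.6-5.8%.

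**Repeated visits.** If two visits were pooled as independent, with an assumed within-person correlation of 0.5, the variance of the arm comparison would grow by a further factor of 1 + 0.5. For mean 12 and SD 5, φ becomes 2.083 × 1.5 = 3.125, which is 26.8%. For mean 40 and SD 15 it becomes 5.625 × 1.5 = 8.44, about 50%. Simulation gave 25% and 50%. The plan does not say whether visits would be pooled.

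**The case against.** The strongest reply is that the Poisson sentence concerns effect sizes, not hypothesis tests. Section 7.6 gives the secondary hypotheses to two-sample t-tests. With arm as the only term, the Poisson estimate is simply a ratio of means and does not depend on dispersion. This stands. A reader might infer that the secondary between-arm conclusions as a whole carry a grossly inflated false-positive rate. The documents do not support that, because the error enters only if a Poisson-based interval or p-value is reported.

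The objection to a single direction of error also stands. A reader might infer that the standard errors are always far too small. They are not: narrow total scores and single items can give a conservative test, and the nightmare survey is analysed only by item. Nor is a count-type model plainly wrong for a question about nightmare frequency. It also cannot be said that the fallback applies exactly when ANOVA assumptions fail, since no criterion is given.

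It can further be said that GEE, mixed models and adjusted models appear in the same section. This does not cure the defect. None is tied to the fallback, baseline is not named as a covariate for the adjusted models, and Poisson is the only stated replacement for ANOVA. A statistician might add a robust variance unprompted, but the plan does not require it.

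**Conclusion.** The point holds as a defect in a conditional fallback for secondary and exploratory outcomes. Followed as written, the fallback gives model-based standard errors that are correct only by coincidence. They are too small for overdispersed total scores and too large for underdispersed scores or items. The sizes in the table illustrate this and are not predictions: every mean is assumed, and the documented SD of 5 belongs to PSQI change, so using it for raw scores is itself an assumption. The sentence should be changed, but it does not threaten the trial's main result. The point estimate, the secondary t-tests, the primary test and the sample size are untouched.

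**What to change.** In protocol section 7.6 and in the SAP, replace the Poisson sentence with the linear mixed model or GEE already named there. Fit it to the questionnaire scores with baseline as a covariate, participant as the cluster and sandwich standard errors.

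If the sponsor prefers to keep Poisson, the minimum is to require robust standard errors clustered by participant. In the single-visit simulation a robust variance alone brought the type I error back to about 5%. An ordinal model for single questions is an option, not a requirement.

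The cost is one sentence in each document, with no new data and no change to the sample size. Intervals for overdispersed total scores will be wider than a plain Poisson fit would print, but that width is the correction itself.

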## **7.7. Implementation**

All statistical analyses will be carried out by the Principal Investigator and/or a PhD Biostatistician.

## **8. Subject Accountability**

Subjects who meet the eligibility criteria and agree to participate will be given written informed consent approved by the center's Institutional Review Board (IRB).

All subjects who meet eligibility criteria and complete the informed consent form are considered enrolled in the study. Screening tests that are part of Standard of Care (SOC) can be used to determine pre-eligibility. Subjects enrolled in this investigation must be followed per this investigational protocol.

### **8.1. Withdrawal**

All subjects enrolled in the clinical study, including those withdrawn from the clinical study or lost to follow-up, shall be accounted for and documented. If a subject withdraws from the clinical investigation, the reason(s) shall be reported. Reasons for withdrawal include, but are not limited to:

- Subject found not to meet eligibility criteria
- Subject choice to withdraw consent
- Investigator discretion
- Enrollment ceiling met
- Lost to follow-up, despite best efforts to locate the subject
- Death (see Section 8.3 for reporting requirements)

If a subject withdraws from the clinical investigation, the reason(s) shall be reported in a study data collection system. Data up to the point of withdrawal will be collected. All open adverse events should be closed or documented as chronic.

## **8.2. Enrollment Controls**

Investigational sites will monitor the number of subjects enrolled and will notify NW when the enrollment goal is close to being reached. Once enrollment ceiling is reached, site staff shall discontinue study enrollments.

## **9. Safety**

### **9.1. Risk/Benefit Assessment**

#### **9.1.1. Known Potential Risks**

There are no predicate devices used specifically to treat nightmares. However, there are many variations of over-the-counter applications and wearable devices that vibrate to signal the wearer. The same risks known to over-the-counter wearable fitness devices apply to this device.

The NW digital therapeutic is designed to interrupt during a nightmare, but not awaken the individual. The device may instead awaken, or incorrectly diagnose a nightmare and alarm (false positive). Therefore, worsening sleep quality is a potential risk of this device intervention.

#### **9.1.2. Known Potential Benefits**

Potential benefits are currently unknown. Uninterrupted sleep due to interrupting nightmares by arousing the subject without waking them, resulting in a more restful sleep, as measured by the PSQI. Improved sleep quality and duration can improve overall psychological effects of sleep deprivation.

#### **9.1.3. Assessment of Potential Risks and Benefits**

Study inclusion and exclusion criteria were designed to only include subjects already suffering from sleep disorder and therefore most likely to benefit from the intervention.

Since the intervention is delivered through a non-invasive smartwatch, study participants may simply discontinue wearing the watch if the intervention is contributing to deteriorating sleep quality.

The trial includes a primary safety endpoint designed to evaluate worsening sleep quality:

1. Epworth Sleepiness Scale

The trial also includes a secondary safety endpoint designed to evaluate worsening suicidal risk:

1. Columbia-Suicide Severity Rating Scale (C-SSRS LT) will be administered at the beginning and end of the study.
  - a. The Lifetime and Recent version will be used to determine if the subject is suitable for this study.
    - i. Potential Subjects that have a rating of “High” will be excluded from this study.

- ii. Since a “High” rating is an imminent safety risk, study staff will immediately call/page the PI, and if needed, a licensed staff member to conduct a safety assessment.
  1. If there isn’t a licensed staff person available, the subject will be TAKEN to the Hospital Emergency Room.
- b. At the 30, 60, and 90 day visits(+7 days), the subject will take another C-SSRS, the Since Last Contact version.
  - i. Either an increase in or a “High” score is an imminent safety risk, so study staff will immediately call/page licensed staff member to conduct a safety assessment.
    1. If there isn’t a licensed staff person available, the subject will be TAKEN to the Hospital Emergency Room.

## **9.2. Unanticipated Problems**

### **9.2.1. Definition of Unanticipated Problems (UP)**

The Office for Human Research Protections (OHRP) considers unanticipated problems involving risks to participants or others to include, in general, any incident, experience, or outcome that meets **all** of the following criteria:

- Unexpected in terms of nature, severity, or frequency given (a) the research procedures that are described in the protocol-related documents, such as the Institutional Review Board (IRB)-approved research protocol and informed consent document; and (b) the characteristics of the participant population being studied;
- Related or possibly related to participation in the research (“possibly related” means there is a reasonable possibility that the incident, experience, or outcome may have been caused by the procedures involved in the research); and
- Suggests that the research places participants or others at a greater risk of harm (including physical, psychological, economic, or social harm) than was previously known or recognized.

This definition could include an unanticipated adverse device effect, any serious adverse effect on health or safety or any life-threatening problem or death caused by, or associated with, a device, if that effect, problem, or death was not previously identified in nature, severity, or degree of incidence in the investigational plan or application (including a supplementary plan or application), or any other unanticipated serious problem associated with a device that relates to the rights, safety, or welfare of subjects (21 CFR 812.3(s)). For this clinical trial, unanticipated problems include, but are not limited to, significant changes in the sleep environment which may impact sleep quality.

### **9.2.2. Unanticipated Problem Reporting**

The principal investigator (PI) will report unanticipated problems (UPs) to the site Institutional Review Board (IRB) and to the sponsor. The UP report will include the following information:

- Report date, IRB Study number, Study Title, Study Staff Contact Information, Date UP occurred, and date PI was notified about the UP.
- Description of the Unanticipated Problem which occurred during the conduct of the research.
- Provide an explanation for why this Unanticipated Problem occurred.
- Characterize the impact of the Unanticipated Problem on the study.

- Describe the steps which have been taken to resolve the reported occurrence.
- Describe the plan implemented to avoid or prevent future occurrences.
- Inform other study participants as necessary.
- Name all other entities to which this UP has been reported.
- Determine if the UP will require modification of the currently approved study and/or consent form.

### **9.2.3. Serious Adverse Event (SAE) Reporting**

A Serious Adverse Event (SAE) is an untoward occurrence in human research that results in death, a life-threatening experience, inpatient hospitalization, prolongation of hospitalization, persistent or significant disability or incapacity, congenital anomaly, or birth defect, or that requires medical, surgical, behavioral, social, or other intervention to prevent such an outcome (VHA Handbook 1058.01§4.r and 21 CFR 312.32(a)).

Only adverse events and deaths occurring at the site that are 1. serious **and** 2. unanticipated **and** 3. related or probably related to the research need to be reported to the IRB (VHA Handbook 1058.01 §6.a. & 6.b.)

If the event satisfies ALL three of these criteria the event must be reported to the IRB **within 5 business days** of learning of the event. The study sponsor will also be notified within the same time frame.

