### **9.2.4. Adverse Event Reporting**

Adverse Events are unfavorable changes in health that occur in trial participants during the clinical trial or within a specified period following the trial.

For this clinical trial, adverse events include any adverse event that occurs as a result of the use or potential use of the study device. An investigator shall submit to the sponsor and to the reviewing Institutional Review Board (IRB) a report of any unanticipated adverse events, no later than 10 working days after the investigator first learns of the effect (21 CFR 812.150(a)(1)). A sponsor who conducts an evaluation of an unanticipated adverse device effect under 812.46(b) shall report the results of such evaluation to the Food and Drug Administration (FDA) and to all reviewing IRB's and participating investigators within 10 working days after the sponsor first receives notice of the effect. Thereafter the sponsor shall submit such additional reports concerning the effect as FDA requests (21 CFR 812.150(b)(1)).

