## **9.3. Death Reporting**

Death is reported as is stated in section 8.2.3 Serious Adverse Event (SAE) Reporting.

A death that meets all three criteria for an SAE, as above, shall be reported by Study Staff to the IRB within 5 business days of learning of the death.

A detailed narrative or death letter may be requested by the sponsor including date of death, place, circumstances, cause of death, and whether the death was witnessed or not.

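### A serious adverse event or death that a site judges anticipated, which could include a suicide attempt, has no timed route to the sponsor

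*Protocol*

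**What the plan says.** Protocol 9.2.3 limits what must go to the IRB. The limiting sentence begins "Only adverse events and deaths occurring at the site that are 1. serious" and adds that the event must also be unanticipated and be related or probably related to the research. It continues: "If the event satisfies ALL three of these criteria the event must be reported to the IRB", with a limit of 5 business days. The next sentence is the only one in the section that concerns the sponsor: "The study sponsor will also be notified within the same time frame".

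Section 9.3 refers deaths back to the SAE section (cited there as 8.2.3; the SAE section is 9.2.3) and repeats the test: "A death that meets all three criteria for an SAE, as above, shall be reported by Study Staff to the IRB within 5 business days". On the sponsor it says only "A detailed narrative or death letter may be requested by the sponsor".

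Section 9.2.4 requires the investigator to send the sponsor and the IRB "a report of any unanticipated adverse events, no later than 10 working days" after learning of the effect. It describes adverse events in two ways. The general statement is "Adverse Events are unfavorable changes in health that occur in trial participants". The trial-specific one is that "adverse events include any adverse event that occurs as a result of the use or potential use of the study device".

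Section 9.2.2 sends unanticipated problems to the site IRB and the sponsor and gives no deadline. Under 9.2.1 such a problem must be unexpected, at least possibly related, and suggestive of greater risk than was known.

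**The concern.** The three-part test is a rule about what an IRB needs to see quickly. Here it also decides what the sponsor is told. This is a multi-site trial, and unanticipated-problem reports go to each site's own IRB and to the sponsor, so the sponsor is the party placed to see serious events across sites. If the site's own judgement of expectedness or relatedness filters events first, a pattern across sites or between arms can go unseen.

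Suicidal behaviour is the case that matters most. The population has PTSD, and suicide risk is a named safety endpoint. The plan does not say whether a suicide attempt is anticipated, and the text points both ways:

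- **Towards unanticipated:** 9.1.1 does not list suicidality as a known risk, and 5.2 excludes people at high risk on the C-SSRS or with a PHQ-9 of 20 or more.
- **Towards anticipated:** 9.2.1 judges expectedness partly by the population under study, and 5.2 makes a positive PHQ-9 suicide item a trigger for assessment, not an automatic exclusion.

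Two sites could class the same event differently, and only one of them would then owe the sponsor a timed report.

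**Working it through.** No arithmetic beyond counting applies. Each route from site to sponsor is set out by deadline and entry condition.

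| Route | Deadline to sponsor | Event must be |
|---|---|---|
| 9.2.3, with 9.3 for deaths | 5 business days | serious, unanticipated, and related or probably related |
| 9.2.4 | 10 working days | unanticipated |
| 9.2.1 and 9.2.2 | none stated | unexpected, related or possibly related, and suggesting greater risk |

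Timed routes: 2. Those open to a serious event or death, by how the site classes it:

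| Site's judgement | 9.2.3/9.3 | 9.2.4 | Timed routes open |
|---|---|---|---|
| Unanticipated, and related or probably related | yes | yes | 2 of 2 |
| Unanticipated, unrelated; 9.2.4 read by its general definition | no | yes | 1 of 2 |
| Unanticipated, unrelated; 9.2.4 read as device-caused only | no | no | 0 of 2 |
| Anticipated, whatever the relatedness | no | no | 0 of 2 |

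The first column rests on reading the sponsor sentence in 9.2.3 as conditional. It says the sponsor is *also* told, in the *same* time frame. Both words need something to refer back to, and the only candidate is the IRB report that is due when all three criteria are met.

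Other parts of the plan were checked for a route that would close the gap:

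- **Sponsor evaluation (9.2.4).** Results go to FDA, all IRBs and all investigators. But the step covers unanticipated device effects, and its clock starts when the sponsor first receives notice. It cannot pick up an event that a site did not send.
- **Interim analyses (7.4).** They cover demographics and the primary endpoint only. Looks with safety content: 0 of 2.
- **C-SSRS and PHQ-9 triggers (6.12 to 6.14, 9.1.3).** They alert the investigator or a licensed clinician at scheduled assessments. They protect the individual but do not require anyone to tell the sponsor.
- **C-SSRS analysis (7.5 and the SAP).** It compares Day 0 with Day 30 in the Active arm, and the SAP's intention-to-treat set is those who complete the study. A participant who dies before Day 30 has no Day 30 score.
- **Withdrawal records (8.1).** Death is a listed reason, entered in the data system with no deadline.
- **Nightly-use monitoring (2.3).** Non-use prompts a contact, which may bring some events to light. It is not a reporting duty.
- **Section 11.** Its deadlines concern protocol deviations, with a passing mention of unanticipated problems, and it does not name the sponsor as recipient.
- **SAP.** It contains no safety-reporting rule.

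Sites named: 4 in Table 2 (Minneapolis, Tampa, Walter Reed, Cleveland) + 1 more in the Synopsis (FBCH) = 5. The Synopsis also refers to multiple VA hospitals, so 5 is a minimum.

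**The case against.** The strongest reply has four parts.

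1. **The sponsor filter is inferred.** The restrictive sentence in 9.2.3 speaks only of the IRB. The sponsor sentence stands apart and does not restate the criteria, and the narrative clause in 9.3 seems to presuppose that the sponsor hears of deaths. The text is indeed not airtight. But the unfiltered reading leaves *also* and *same time frame* with nothing to refer to, and wording that sites can read two ways on this subject needs correcting anyway.

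2. **A suicide attempt would probably be called unanticipated.** The known-risk list omits suicidality, high-risk people are screened out, and the population wording sits only in the unanticipated-problem definition, not in 9.2.3 or 9.2.4. If the attempt is so classed, 9.2.4 carries it to the sponsor within 10 working days, at least under the general definition. This stands as a point about likelihood. It does not remove the gap, because the plan leaves the classification to each site.

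3. **Other commitments apply.** Section 15 commits the trial to ICH GCP and the applicable federal regulations, and 9.2.3 and 9.2.4 cite their sources for the filters. What those sources require cannot be checked from these documents. A general commitment supplies no sponsor deadline in the text, while Section 9 gives sites specific and narrower instructions. The Synopsis also provides for transfer of de-identified data to the sponsor, again without a deadline.

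4. **The device is a non-invasive vibrating watch, and the fix names nobody to review pooled events.** Both are fair. Notice alone does not guarantee review, but no cross-site review can start without it.

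**Conclusion.** The concern holds. As written, no timed route to the sponsor exists for an SAE or death that a site judges anticipated (0 of 2). For one judged unanticipated but unrelated, the count is 1 of 2 or 0 of 2, depending on the reading of 9.2.4. The conclusion rests on two things: the natural reading of the sponsor sentence in 9.2.3, and a site in fact making the anticipated or unrelated call. The documents give no event rate and none is assumed, so the number of events that would be missed or delayed is unknown. This should be corrected as a participant-safety matter. It does not affect the efficacy analysis, the sample size or the type I error.

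**What to change.** Keep the three-part test for expedited reporting to the IRB. In 9.2.3 and 9.3, replace the dependent sponsor sentence with a free-standing duty, for example:

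> Sites will notify the sponsor of every SAE, every death and all suicidal behaviour, whatever the expectedness or relatedness, within 5 business days of becoming aware of it.

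The change is to protocol wording only and uses the 5-business-day window already in place. The cost is that the sponsor will receive some reports of unrelated events and sites will have slightly more reporting work.
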